## 9) Data Management\*

We will perform a superiority test and examine the mean pain score differences at time points 2 hours and 24 hours after surgery as our primary outcome. A t test or Mann Whitney U will be performed to compare the means depending on the distribution of the data with confidence intervals. Secondary outcomes include postop nausea and vomiting scores and morphine equivalents received. We will compare these scores between groups similarly using t test or Mann Whitney U with confidence intervals.

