**6-Oxycodone 5mg every 4 hours as needed for pain during the first 1-2 weeks postop**

After surgery, patients will be evaluated for the primary outcome of pain status at time points 2 hours and 24 hours using the numeric rating pain scale (0-10). Patient's nausea and vomiting will be evaluated by using a binary "yes" or "no" for nausea and recording the number of episodes of vomiting. The Apfel score will be used during statistical analysis to explore possible causes for differences in nausea and vomiting (0-4). Opioid consumption will also be recorded during the first 24 hours and converted to morphine milliequivalents using patient medical records. Patient data will then be compiled for statistical analysis.

Patients will be assessed routinely once every hour by the circulating nurse for the duration of their care in the hospital. Should a patient receive ambulatory care and depart from the hospital before 24 hours have elapsed, they will be contacted via telephone for assessment using the numeric rating pain scale (1-10) and post-op nausea and vomiting.

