## **7) Study Design**

- The primary purpose of this project is in the treatment of pain around the immediate post-operative time after total knee replacement surgery. As a parallel experimental/interventional study design, patients will be randomized to either the control group (institution specific joint replacement pain protocol) or the intervention group (receiving the postoperative adductor canal block). Patients and those collecting the postoperative data will be blinded to eliminate bias in a 1:1 randomization process matching intervention group patients with control group patients. The surgeon will not be informed

ahead of time regarding which cohort a patient belongs to in an effort to reduce bias, though during the procedure may become privy to the group due to when the anesthesiologist places the block. The anesthesiologist will be informed the night before the respective procedure as to which group the patient was randomized into by one of the other non-primary surgeon members of the team. The randomization will be done using a random number generator. We aim to enroll 84 patients. If interested, the subject will be allowed to find out their group assignment when the study is over.

- Power Analysis:

Study Group Design: Two independent study groups

Primary Endpoint: Continuous

Data normally distributed

Alpha: 0.05

Power: 0.80

Total number of patients enrolled: 84

Based on similar study design [10], the standard deviation for pain scores was 3. Assuming a reasonable clinically significant difference of 2 on VAS score, this calculates to sample size of 35 in each group. Assuming attrition rate of 20%, 42 samples in each group will be obtained

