## 8) Study Endpoints\*

- *Primary endpoint – change in pain score at time points 2 hours and 24 hours after primary total knee arthroplasty for each group. The numeric pain rating scale will be used- a higher pain score would indicate higher pain levels. It is scaled from 0-10.*
- *Secondary endpoint - (1) Total opioid consumption in the immediate post-operative period (preoperative block versus postoperative block) (2) change in patient nausea scores and vomiting scores at time points 2 hours, and 24 hours (3) duration of hospital stay.*

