### *INTERIM ANALYSIS:*

We plan to analyze this trial for futility by employing the O'Brien and Fleming method of interim analysis. Specifically, we will analyze our groups at interims n = 21 (total 42) for futility using

appropriate boundaries for the mean difference. Should the mean difference exceed the boundary, the trial will conclude concluding significance between the groups; conversely, should the mean difference be below the boundary, the trial will terminate with futility.

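### Pain at 2 h and pain at 24 h are both primary, but no rule says which decides success: depending on the rule, either the 5% error or the 80% power is not met

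*Combined protocol and SAP*

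**What the plan says.** All references are to the combined protocol and SAP.

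- Section 5 (Procedures Involved) describes the "primary outcome of pain status at time points 2 hours and 24 hours".
- Section 8 (Study Endpoints) gives the primary endpoint as "change in pain score at time points 2 hours and 24 hours after primary total knee arthroplasty for each group". It ranks neither time above the other.
- Section 9 (Data Management) states "We will perform a superiority test" and will "examine the mean pain score differences at time points 2 hours and 24 hours after surgery as our primary outcome". The method is a t test or a Mann-Whitney U test. No repeated-measures model, average over time, testing order or multiplicity adjustment is given.
- Section 7 (Study Design, Power Analysis) has one alpha of 0.05 and one power of 0.80. On variability it says "the standard deviation for pain scores was 3", and on effect and size "Assuming a reasonable clinically significant difference of 2 on VAS score, this calculates to sample size of 35 in each group". Adding 20% for attrition gives 42 per arm, 84 in total.
- The interim part of section 9 stops or continues on a mean difference at 21 per arm, without naming the time at which it is measured.

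**The concern.** Two primary comparisons need a rule that turns two results into one conclusion, and the plan has none. The three possible rules have different properties:

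- **One named time point decides.** The section 7 calculation fits this rule, but no time point is named.
- **Either is enough.** There are two chances to succeed by accident, and alpha is not shared between them.
- **Both are needed.** There are two chances to fail, and the sample size was set for one.

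The two times may well disagree. Section 3 (Background) argues that a block given at the end of surgery could extend pain relief further into recovery, so the effect need not be the same at 2 h and 24 h. If one time is significant and the other is not, the plan does not say whether the trial succeeded, and the rule could be chosen after the data are seen. The same gap affects the interim look: if the two times fall on opposite sides of the boundary, the text gives no determinate action.

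**Working it through.** **Inputs from section 7:** difference 2, SD 3, alpha 0.05, power 0.80, 35 evaluable and 42 enrolled per arm.

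**Assumptions, not in the documents:** correlation ρ between the two test statistics from 0 to 0.9; the true difference at each time, as listed below; two-sided testing; the trial runs to full size with the interim look set aside. The calculations use the normal approximation.

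**Step 1. Reproduce the plan's figure.** n per arm = 2 × [3 × (1.960 + 0.842) / 2]² = 35.3. The one-sided version, with 1.645 in place of 1.960, gives 27.8. The stated 35 therefore fits a single two-sided comparison. The drift at 35 per arm is (2/3) × √(35/2) = 2.789, and power is Φ(2.789 − 1.960) = 0.796 (0.785 by exact t).

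**Step 2. Either time counts.** With no effect at either time, family-wise error = 1 − P(|Z₁| < 1.96 and |Z₂| < 1.96). At ρ = 0 this is 1 − 0.95² = 0.0975.

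**Step 3. Both must win.** Power = P(Z₁ > 1.96 and Z₂ > 1.96), where Z₁ and Z₂ are bivariate normal with mean (difference/3) × √(n/2) and correlation ρ. The drifts at 35 per arm are 2.092 for a difference of 1.5, 2.789 for 2, 3.486 for 2.5 and 4.183 for 3. At 42 per arm the drift for a difference of 2 is 3.055. At ρ = 0, with a difference of 2 at each time and 35 per arm, power is 0.796² = 0.634.

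| Quantity | ρ = 0 | 0.5 | 0.7 | 0.9 |
|---|---|---|---|---|
| Error, either counts | 0.0975 | 0.0907 | 0.0835 | 0.0704 |
| Power, both; 2 and 2; 35 per arm | 0.634 | 0.682 | 0.708 | 0.746 |
| Power, both; 2 and 1.5; 35 per arm | 0.440 | 0.498 | 0.524 | 0.548 |
| Power, both; 2 and 2.5; 35 per arm | 0.746 | 0.769 | 0.781 | 0.794 |
| Power, both; 2 and 3; 35 per arm | 0.786 | 0.793 | 0.795 | 0.796 |
| Power, both; 2 and 2; 42 per arm | 0.745 | 0.777 | 0.796 | 0.824 |

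**Step 4. Check with t tests.** Simulation of 200,000 trials per scenario gives error of 0.097 to 0.071 and, for both with equal differences of 2 at 35 per arm, power of 0.616 to 0.733. The normal approximation slightly flatters the power.

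**The case against.** **Separate tests are an inference.** Sections 7 and 9 use the singular for the endpoint and the test, and section 8 speaks of a change without giving a baseline. This stands in part. Separate tests at each time are the most natural reading of the plural differences in section 9, but they are not spelled out. The defect is the missing rule; inflated error follows under only one way of filling it.

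**The two harms exclude each other.** This stands. If either time is enough, power is not the problem; if both are needed, error stays at or below 5%. A reader might infer that the trial runs at nearly 10% error and is also underpowered. The documents do not support that.

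**Equal effects might be taken as the best case.** They are not. A longer-lasting benefit is as compatible with a later difference above 2 as with one below 2 at either time. Differences of 2 and 3 give 0.786 to 0.796 at 35 per arm. The documents give no effect by time, so 0.63 to 0.75 is one scenario.

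**It is tempting to say that only a single named time point could deliver 5% error and 80% power.** That goes too far. An adjusted procedure or one combined test could also do so. The interim look matters too: read literally, it ends the trial at 21 per arm on either side of the boundary. Single-comparison power there is about Φ((2/3) × √(21/2) − 1.960) = Φ(0.200) = 0.58 at an unadjusted 0.05, even with one time point named.

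**Follow-up lasts only 24 h, so all 42 per arm might be evaluable.** Power for both is then 0.75 to 0.82, reaching 0.80 only near the top of the correlation range. Section 7 itself plans for 20% attrition.

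**One-sided testing may have been meant.** The stated 35 does not fit it. If it was, error when either counts is still 6.8% to 9.75%, while power for both at 35 per arm rises to 0.76 to 0.84.

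**Conclusion.** The point holds: the primary analysis has two comparisons, one undivided alpha, a sample size for one comparison, and no rule for success. It should be fixed before the trial reports or any comparative data are seen.

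The size depends on the rule the sponsor has in mind. The figures below are for separate unadjusted two-sided tests, the full trial and ρ between 0 and 0.9:

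- **Either counts:** family-wise error of 7.0% to 9.75% in place of 5%, when there is no effect at either time.
- **Both required:** error controlled. Power at 35 per arm is 0.63 to 0.75 for differences of 2 and 2, 0.44 to 0.55 for 2 and 1.5, and 0.75 to 0.79 for 2 and 2.5. With all 42 per arm evaluable and 2 at each time, it is 0.75 to 0.82.

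That no rule is written can be read directly from sections 5, 7, 8 and 9. The exact figures are less certain, because the correlation and the effect at each time are assumed.

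**What to change.** Before any comparative data are seen, including at the interim look, name one time point in sections 7, 8 and 9 as primary. The choice is the sponsor's. That time point carries the alpha of 0.05, the power statement and the interim decision. Test the other time only if the first is significant, within the same overall alpha.

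**Cost:** no added patients, only text edits. The second time point can be claimed only if the first is significant.

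**Acceptable alternatives,** at 35 per arm with a difference of 2 at each time, ρ from 0 to 0.9 and the interim look set aside:

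- Holm across the two times: power 0.91 to 0.77 for at least one time.
- One test on the mean of the two scores: power 0.98 to 0.82, falling to 0.84 to 0.57 if the difference at one time is 1.
- Require both: restate the power as about 0.63 to 0.75 under equal effects, or re-justify the size. Power of 0.80 needs about 47 (ρ = 0) down to 40 (ρ = 0.9) evaluable per arm.

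The interim part of section 9 says "We plan to analyze this trial for futility by employing the O'Brien and Fleming method of interim analysis" and also "Should the mean difference exceed the boundary, the trial will conclude concluding significance between the groups". Whether that look is for futility or efficacy, and what its boundaries are, is a separate point. Here it is enough that it uses the named time point.

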## 5) Procedures Involved\*

Study design: All patients who fulfill inclusion criteria, including undergoing a pregnancy test if a woman of childbearing age, undergoing total knee arthroplasty will be randomized to one of two groups to be given the standard orthopaedic joint replacement protocol including general anesthesia with the preoperative adductor canal block **or** the standard orthopaedic joint replacement protocol including general anesthesia except the adductor canal block will be given at the end of the procedure instead of the beginning. General anesthesia for the groups will be standardized, and no intraoperative analgesics given. Nerve blocks will be placed for both groups by anesthesiologists as is the standard protocol. All nerve blocks will be placed following the same procedural protocol with the same supplies under ultrasound guidance to ensure consistency and minimize variation. Nerve blocks in both groups will include the standard 20mL Ropivacaine 0.2% (local anesthetic) injected in the same manner. PACU orders will not differ between the groups and will be the standard procedure for total joint arthroplasty at the facility. Cases will be assigned randomly in a 1:1 fashion. A computer program such as Microsoft Excel will be employed for the randomization process.

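### The plan allows for 20% attrition but names only tests that drop missing 24-hour pain scores; if loss is related to pain and differs by arm, the 24-hour comparison may be biased, and a joint model with the 2-hour score would reduce this.

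*Combined protocol and SAP*

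**What the plan says.** Section 9 announces a superiority comparison ("We will perform a superiority test") of mean pain at 2 and 24 hours as the primary outcome. The method is "A t test or Mann Whitney U will be performed to compare the means depending on the distribution of the data with confidence intervals". No section defines an analysis set, a method for missing scores or a sensitivity analysis.

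The power analysis in section 7 allows for loss: "Assuming attrition rate of 20%, 42 samples in each group will be obtained". This is a single overall figure, with no cause or time point attached.

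Section 5 provides follow-up for early leavers: "Should a patient receive ambulatory care and depart from the hospital before 24 hours have elapsed, they will be contacted via telephone". The background (section 3) says that more pain can lengthen the hospital stay, and section 8 makes length of stay a secondary endpoint.

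**The concern.** A t test or Mann-Whitney U at 24 hours needs a 24-hour score. With nothing else specified, patients without one leave the comparison even if their 2-hour score is on file.

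The documents make pain-related loss plausible. If pain prolongs the stay, patients with little pain go home sooner, and those who go home depend on a telephone call. If one block timing gives better early analgesia, that arm may send more low-pain patients home and may lose more of them.

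At stake is one of the two primary time points. A real 24-hour difference could be diluted. A difference present only at 2 hours could appear at 24 hours as a small disadvantage for the arm that did better early.

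**Working it through.** **Inputs from the documents.** Difference 2 ("Assuming a reasonable clinically significant difference of 2 on VAS score"), SD 3 ("the standard deviation for pain scores was 3"), alpha 0.05, power 0.80, equal allocation ("Cases will be assigned randomly in a 1:1 fashion"), 20% attrition. Sidedness is not stated. Two-sided is assumed, because one-sided gives 28 per arm and does not match the plan's 35.

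**1. The plan's own figure.** n per arm = 2 × [SD × (1.96 + 0.8416) / difference]² = 2 × (3 × 2.8016 / 2)² = 35.3. The plan says "this calculates to sample size of 35 in each group", which agrees before rounding up. Then 35 × 1.2 = 42, as stated.

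**2. Power if loss is unrelated to pain.** 42 × 0.8 = 33.6 per arm remain.

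| Loss | Remaining per arm | Power, normal | Power, t test |
|---|---|---|---|
| 0% | 42 | 86.3% | 85.5% |
| 10% | 37.8 | 82.6% | 81.6% |
| 20% | 33.6 | 78.0% | 76.8% |

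The shortfall of 2 to 3 points from 80% at 20% loss arises mostly from multiplying by 1.2 rather than dividing by 0.8 (35 / 0.8 = 43.75, or 44). That is a sample-size matter, not bias.

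**3. Direction of bias, by arithmetic.** Let the lost patients in each arm average g points below those retained in the same arm. The retained mean then exceeds the arm's true mean by g × (loss fraction), so

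observed difference = 2 − g × (loss in better arm − loss in worse arm).

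| Loss, better / worse arm | g = 1 | g = 2 | g = 3 |
|---|---|---|---|
| 20% / 20% | 2.0 | 2.0 | 2.0 |
| 25% / 15% | 1.9 | 1.8 | 1.7 |
| 30% / 10% | 1.8 | 1.6 | 1.4 |
| 10% / 30% | 2.2 | 2.4 | 2.6 |

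The sign depends on which arm loses more low-pain patients. With equal loss of the same pattern the bias is zero. The loss rates by arm and g are assumptions; the documents give neither.

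**4. A full scenario, by simulation.** Assumptions: 42 per arm; normal scores with SD 3; true difference 2 at both times; correlation between 2-hour and 24-hour scores 0.3 to 0.7; probability of a missing 24-hour score higher when the 2-hour score is low (log-odds slope 0.3 to 1.0 per point). At 20% overall loss the arms lose about 24–28% (better) and 12–16% (worse).

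| Setting | t test on observed scores | Joint estimate from both times |
|---|---|---|
| 20% loss, driven by 2-hour pain | 1.57–1.94, power 0.64–0.74 | 1.98–2.00, power 0.77–0.80 |
| 5–10% loss, driven by 2-hour pain | 1.74–1.98 | not tabulated |
| 20% loss, random | unbiased, power about 0.77–0.79 | unbiased, smaller variance |
| 20% loss, driven by 24-hour pain | 1.41–1.83 | 1.65–1.85 |

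With a 2-point effect at 2 hours, none at 24 hours, and 20% loss driven by 2-hour pain, the t test makes the arm that did better early look about 0.03 to 0.43 points worse at 24 hours.

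**5. Gain under random loss.** With 20% missing and correlation ρ, the variance of the joint estimate relative to the t test is [ρ² + (1 − ρ²)/0.8] / (1/0.8) = 1 − 0.2ρ². For ρ = 0.3, 0.5 and 0.7 this is 0.98, 0.95 and 0.90, a reduction of about 2 to 10%.

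**The case against.** The case against has four parts.

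- **Telephone follow-up.** The plan aims calls at exactly the patients in question. Bias needs early departure, a failed call, a link between the failed call and pain, and unequal loss between arms. This stands. If calls succeed often enough to leave only 5 to 10% missing, the t test estimates about 1.7 to 2.0, and the problem is modest.
- **The meaning of 20%.** A reader might infer that one patient in five will lack a 24-hour score. The documents do not support this. The figure is total attrition and could include cancelled surgery or withdrawal before any score. Such patients cannot be recovered by any model of the observed scores.
- **Direction and power.** A reader might infer that the 24-hour effect must be biased in favour of the worse arm, or that power falls from 80% to the lower figures because scores are missing. Neither follows. The direction is conditional (step 3). The fair baseline at 20% loss is about 77%, not 80%.
- **The remedy favours itself.** Loss that depends only on the 2-hour score is the pattern a joint model corrects fully. If loss follows unseen 24-hour pain, correction is partial, and at correlation 0.3 it is almost nil. A normal-theory model on a 0–10 score also gives up the rank test as the primary analysis. Both points stand as limits. Even so, in the settings examined the joint estimate was never materially worse than the t test.

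The plan also does not say that it will analyse only patients with a score. That is what the named tests do when nothing else is specified.

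**Conclusion.** The point holds in conditional form. The plan expects attrition, makes 24-hour pain a primary time point, and names only tests that by default ignore patients without that score and make no use of their 2-hour score. Whether this biases the result depends on the failed-call rate, its relation to pain and its balance between arms, none of which the documents give.

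If the whole 20% fell at 24 hours and followed 2-hour pain, a true difference of 2 would be estimated at about 1.6 to 1.9, with power about 0.64 to 0.74 against about 0.77 to 0.79 for random loss. At 5 to 10% loss the estimate is about 1.7 to 2.0. These figures are scenarios, not predictions. They rest on normal scores, SD 3, equal effects at both times and correlations of 0.3 to 0.7. The change is worth making because it is cheap, uses data already collected, and helps or does no material harm under every loss pattern examined.

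**What to change.** In section 9:

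1. Make the primary analysis one mixed model for repeated measures of the 2-hour and 24-hour pain scores, with arm, time and arm-by-time, and an unstructured covariance. Read each time point's arm difference and confidence interval from it.
2. Define the analysis set as all randomised patients who have surgery and any pain score, in the arm assigned.
3. Keep the t test or Mann-Whitney U on observed scores as a sensitivity analysis.
4. Report the number of missing scores by arm and time point.
5. Add an analysis in which missing 24-hour scores are shifted 1 and 2 points lower, since those lost may be the patients with less pain.

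The cost is SAP wording and a standard model, with no extra patients or data. The analysis becomes slightly more complex and relies on normal theory for a bounded 0–10 score. It cannot recover patients with no score, and corrects only partly if loss depends on unseen 24-hour pain; items 3 to 5 let the reader judge how much that matters.

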### *INTERIM ANALYSIS:*

We plan to analyze this trial for futility by employing the O'Brien and Fleming method of interim analysis. Specifically, we will analyze our groups at interims n = 21 (total 42) for futility using

appropriate boundaries for the mean difference. Should the mean difference exceed the boundary, the trial will conclude concluding significance between the groups; conversely, should the mean difference be below the boundary, the trial will terminate with futility.

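### As written, the interim rule ends the trial at 42 patients whatever the result: one unnumbered boundary decides both significance and futility, and nothing leads on to the planned 84

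*Combined protocol and SAP*

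**What the plan says.** The interim analysis paragraph in section 9 (Data Management) names the O'Brien and Fleming method and sets one look: "we will analyze our groups at interims n = 21 (total 42) for futility". It refers to "appropriate boundaries for the mean difference" but gives no value for any of them. Two actions follow, both tied to a single boundary:

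- Above it: "Should the mean difference exceed the boundary, the trial will conclude concluding significance between the groups".
- Below it: "conversely, should the mean difference be below the boundary, the trial will terminate with futility".

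The power analysis in section 7 (Study Design) assumes alpha 0.05, power 0.80, SD 3 and a difference of 2 points. It reports that "this calculates to sample size of 35 in each group" and, after a 20% allowance for attrition, "Total number of patients enrolled: 84". It does not mention the look.

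Section 8 defines the primary endpoint as "change in pain score at time points 2 hours and 24 hours after primary total knee arthroplasty". Section 9 says "We will perform a superiority test and examine the mean pain score differences at time points 2 hours and 24 hours" and gives the final comparison as a t test or Mann-Whitney U, with no level adjusted for the look.

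**The concern.** Two outcomes around one cut-off leave no region in which the trial continues. Apart from an exact tie, every interim result is terminal. That contradicts the planned 84 patients and makes the stated power unattainable.

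The paragraph also describes the look as one for futility, yet lets it conclude significance. It does not say whether the 2-hour or the 24-hour difference drives the decision, or in which direction. The two time points could give opposite instructions.

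If the team follows the text, the second half of the trial is never run. If it departs from the text, the futility boundary, the information fraction, the sidedness and the time point are settled when interim data are already visible. Which error is likelier depends on the missing number: a high boundary usually calls a real 2-point difference futile, and a low one declares significance with an inflated type I error.

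**Working it through.** **Inputs.** From section 7: SD 3, difference 2, alpha 0.05, power 0.80, 35 per group raised to 42. From the interim paragraph: a look at 21 per arm. Assumptions: normal approximation, and all 21 per arm evaluable unless stated.

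**1. The plan's own figure.** n per group = 2(z_alpha + z_beta)² / (difference/SD)².
- Two-sided: 2(1.960 + 0.842)² / (2/3)² = 35.3.
- One-sided: 27.8.

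The plan says 35, so two-sided alpha is assumed, although the plan does not state it. Then 35 × 1.2 = 42 per arm, or 84. After 20% attrition, 42 × 0.8 = 33.6, about 34 evaluable per arm.

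**2. What 21 per arm can deliver.** SE = 3 × √(2/21) = 0.926. The expected Z for a true 2-point difference is 2/0.926 = 2.160. One cut-off can give both alpha and power only if z_alpha + z_beta is at most 2.160.
- Two-sided: 1.960 + 0.842 = 2.802, too large. Power at 1.96 is Φ(2.160 − 1.960) = 58%. Power of 80% needs z = 2.160 − 0.842 = 1.32, which is two-sided alpha 0.19.
- One-sided: 1.645 + 0.842 = 2.487, too large. Power at 1.645 is 70%. Power of 80% needs alpha 0.094.

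**3. O'Brien-Fleming values.** Solve P(|Z1| ≥ c/√t or |Z2| ≥ c) = 0.05, with correlation √t between looks.
- t = 21/42 = 0.5: interim 2.797, final 1.977.
- t = 21/35 = 0.6: interim 2.572, final 1.992.
- One-sided 0.05: interim 2.373 (t = 0.5) or 2.188 (t = 0.6).

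**4. The literal rule under a true 2-point difference.** P(significance) = Φ(2.160 − z); every other result is called futile.

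| Boundary taken as | z | Points (z × 0.926) | Significant | Futile |
|---|---|---|---|---|
| O'Brien-Fleming, two-sided, t = 0.5 | 2.797 | 2.59 | 26% | 74% |
| O'Brien-Fleming, two-sided, t = 0.6 | 2.572 | 2.38 | 34% | 66% |
| O'Brien-Fleming, one-sided, t = 0.5 | 2.373 | 2.20 | 42% | 58% |
| O'Brien-Fleming, one-sided, t = 0.6 | 2.188 | 2.03 | 49% | 51% |
| Unadjusted two-sided | 1.96 | 1.81 | 58% | 42% |
| Beta-spending futility type | 0.68 | 0.63 | 93% | 7% |

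The break-even boundary is z = 2.160, or 2.0 points. With 17 evaluable per arm (SE 1.029, expected Z 1.944), the 2.797 boundary calls 80% of such trials futile.

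The 0.68 comes from spending 0.070 of beta 0.20 at half information: 2.160 − 1.476. Used as the only cut-off, it has two-sided type I error of about 0.50. Other pairings of beta, expected Z and information fraction put this boundary between about 0.35 and 0.87, with type I error between 0.72 and 0.39.

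**The case against.** The method's name, the plural wording on boundaries and the enrolment of 84 all suggest a standard two-look design whose last sentence was badly written. On that reading the efficacy and final values follow from the method once sidedness and information fraction are fixed, so not everything is open. The percentages are scenarios, because the plan supplies no boundary. The beta-spending row in particular shifts with its inputs.

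Much of this stands. The intention was probably conventional, and the table shows mainly that the rule is undefined. But the decision sentence is the operative rule, and it says the opposite of such a design. Reaching 2.797 and 1.977 requires assuming two-sided alpha, half information and an efficacy use, while the paragraph describes a futility look. No futility boundary follows from the method's name, and nothing in the plan picks the time point. The result in step 2 needs no assumed boundary: no single cut-off at 21 per arm meets both design targets.

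**Conclusion.** The concern holds. Followed as written, the rule stops the trial at 42 patients and defeats the planned 84 and the 0.80 power. At 21 evaluable per arm, a test at two-sided 0.05 has 58% power. With the two-sided O'Brien-Fleming efficacy value at half information as the only boundary, a real 2-point difference would be declared futile in 74% of trials. These figures rest on SD 3, a difference of 2, the normal approximation and two-sided alpha. The one-sided version reaches the same conclusion (70% power). This must be corrected before the interim look, because a boundary chosen afterwards cannot be defended as prespecified.

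**What to change.** Replace the decision sentence with a three-outcome rule, and name the sidedness, the direction and the time point that drive it:

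1. Stop for efficacy only at the O'Brien-Fleming boundary (|Z| ≥ 2.797 at half information, two-sided).
2. Stop for futility only below a separate, lower, non-binding boundary. An example is |Z| < 0.5, which is 0.46 points at 21 per arm. This example is symmetric and would continue after a clearly adverse result, so the sponsor may prefer a directional limit.
3. Otherwise continue to 84 and test at the matching final value (1.977).

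Recompute both values at the actual information fraction. At 0.6 they are 2.572 and 1.992; keeping 1.977 there gives alpha 0.0516. If only futility is intended, delete the significance clause, add the continuation rule and keep 0.05 for the final test.

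**Cost.** Text changes plus a few design decisions before the look, and a little power (look at half information, difference 2):

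| Design | 42 evaluable per arm | 35 | 34 |
|---|---|---|---|
| No look | 0.863 | 0.796 | 0.785 |
| Three outcomes, |Z| < 0.5 for futility | 0.846 | 0.777 | 0.765 |
| Futility only, |Z| < 0.5 | 0.848 | 0.779 | 0.768 |

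Power at 35 is 0.785 under the three-outcome rule if the look falls at 21 of 35. Most of the shortfall from 0.80 after attrition exists without any look; the rule adds about 0.02. Power should be restated. The example limit wrongly stops a true 2-point effect 4.5% of the time at 21 per arm, and 6.7% at 17. Type I error is 0.047 to 0.049 if the futility stop is obeyed and 0.05 if it is ignored.

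This error control covers one time point. If both 2 h and 24 h stay primary, state whether success at either is enough or both are required. If either is enough, the untreated chance of a false positive lies between 0.05 and 1 − 0.95² = 0.0975, depending on their correlation. Splitting alpha (0.025 each, no look) gives power of 0.79 at 42 per arm and 0.69 at 34. If both are required, no alpha split is needed, but power falls.
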